### **6.3.1.2 Serious Adverse Event:**

An SAE is any AE occurring at any dose that results in any of the following outcomes: death, a life-threatening AE, inpatient hospitalization or prolongation of existing hospitalization, a persistent or significant disability/incapacity, or a congenital anomaly/birth defect. Important medical events that may not result in death, be life-threatening, or require hospitalization may be considered an SAE when, based upon appropriate medical judgment, they may jeopardize the patient or subject and may require medical or surgical intervention to prevent one of the outcomes listed in this definition (See Section 6.3.1.4 for procedures for reporting an SAE).

Allergan considers all cancer AEs as SAEs. In addition, Allergan considers any abortion (spontaneous or nonspontaneous) as an SAE.

Pre-planned surgeries or procedures for pre-existing, known medical conditions for which a patient requires hospitalization is not reportable as an SAE. Any pre-planned surgery or procedure should be clearly documented in the site source documents by the medically qualified investigator at the time of the patient's entry into the study. If it has not been documented at the time of the patient's entry into the study, then it should be documented as an SAE and reported to Allergan.

### **6.3.1.3 Reporting Adverse Events**

Any AE must be recorded in the appropriate eCRF.

All AEs that are drug-related and unexpected (not listed as treatment-related in the current Investigator's Brochure) must be reported to the governing Institutional Review Board/Independent Ethics Committee (IRB/IEC) as required by the IRB/IEC, local regulations, and the governing health authorities. Any AE that is marked "ongoing" at the posttreatment visit must be followed up as appropriate.

### **6.3.1.4 Reporting Serious Adverse Events**

Any SAE occurring during the study period (beginning with informed consent) and for at least 30 days after the last dose of study drug must be immediately reported but no later than 24 hours after learning of an SAE. Serious AEs must be reported directly to Allergan in the US and Canada as listed on the Allergan Study Contacts Page and recorded on the SAE form. All subjects with an SAE must be followed up and the outcomes reported. The investigator must supply the sponsor and the IRB/IEC with any additional requested information (e.g., autopsy reports and discharge summaries).

In the event of an SAE, the investigator must:

1. Notify Allergan/ [REDACTED] immediately by fax or email using the SAE form (contact details can be found on page 1 of the SAE form); phone numbers and relevant Allergan personnel contacts are also on the front page of protocol and Study Contacts Page.
2. Obtain and maintain in his/her files all pertinent medical records, information, and medical judgments from colleagues who assisted in the treatment and follow-up of the subject.

3. Provide Allergan/ [REDACTED] with a complete, written description of the AE(s) on the SAE form describing the event chronologically, including any treatment given (e.g., medications administered, procedures performed) for the AE(s). Summarize relevant clinical information about the event: signs, symptoms, diagnosis, clinical course and relevant clinical laboratory tests, etc. Include any additional or alternative explanation(s) for the causality which includes a statement as to whether the event was or was not related to the use of the investigational drug.

4. Promptly inform the governing IRB/IEC of the SAE as required by the IRB/IEC, local regulations, and the governing health authorities.

### **6.3.1.5 Assessment of Severity**

A clinical determination will be made of the intensity of an AE. The severity assessment for a clinical AE must be completed using the following definitions as guidelines:

Mild	Awareness of sign or symptom, but easily tolerated.
Moderate	Discomfort enough to cause interference with usual activity.
Severe	Incapacitating with inability to work or do usual activity.
Not applicable	In some cases, an AE may be an “all or nothing” finding which cannot be graded.

### **6.3.1.6 Assessment of Causality**

A determination will be made of the relationship (if any) between an AE and the study drug or study procedure, as applicable. A causal relationship is present if a determination is made that there is a reasonable possibility that the AE may have been caused by the drug or study procedure.

If an AE is deemed related to study treatment, the investigator will be asked to further delineate whether the AE was related to the administration procedure (versus the study drug).

Note: a study procedure occurring during the screening/baseline period can include a washout of medication or introduction of a run-in medication or study required diagnostic procedure.

### **6.3.2 Investigator Required Contact to Patient**

#### **6.3.2.1 Investigator Required Contact to Patient for Diary-Confirmed Constipation**

As previously noted, the ePRO system will notify the investigator if a patient reports not having a bowel movement for 4 consecutive days (i.e., diary-confirmed constipation). Once notified the investigator must contact the patient to review his/her status as soon as possible. An unscheduled visit to further evaluate the patient's status should be arranged if deemed warranted by the investigator. The decision to continue, interrupt or permanently discontinue study drug will be left to the discretion of the investigator on a patient-by-patient basis.

The investigator should consider permanent discontinuation of study drug should a patient not have a bowel movement for more than 7 consecutive days or have more than one episode of diary-confirmed constipation.

If a decision to permanently discontinue study drug due to diary-confirmed constipation is made, the patient should be brought in immediately for study termination procedures.

#### **6.3.2.2 Investigator Required Contact to Patient for Frequent Use of Loperamide Rescue Medication**

During the double-blind Treatment period and the posttreatment period, patients may use loperamide rescue medication for the acute treatment of uncontrolled diarrhea as described in Section 5.9. The ePRO system will notify the investigator of patients requiring >4 unit doses over a continuous 24-hour time period (8 mg/day), >7 unit doses over a continuous 48-hour time period (14 mg over 2 days), or >11 unit doses over a continuous 7-day time period. Once notified the investigator must contact the patient to review his/her status as soon as possible.

An unscheduled visit to further evaluate the patient's status should be arranged if deemed warranted by the investigator. A decision to permanently discontinue study drug due to

excessive use of loperamide rescue medication will be left to the discretion of the investigator on a patient-by-patient basis.

[REDACTED]

[REDACTED]

[REDACTED]

[REDACTED]

[REDACTED]

[REDACTED]

[REDACTED]

[REDACTED]

#### **6.4 Safety Monitoring Committee**

No safety monitoring committee will be used for the study.

## **6.5 Pregnancy**

Pregnancy tests will be performed for all women according to local procedures unless they are surgically sterile or there is a documented history of their postmenopausal status. A serum pregnancy test will be performed at screening and urine pregnancy tests will be performed at all other visits through week 12 (or early withdrawal visit), unless a serum pregnancy test is preferred at the discretion of the investigator or if required by local regulations. Additional serum or urine pregnancy tests may be conducted throughout the study in sufficient number, as determined by the investigator or required by local regulation, to establish the absence of pregnancy. If positive, the patient is not eligible to enter or continue in the study.

Any pregnancy that occurs after the first dose of study drug or within 30 days of the last dose of study drug must be immediately reported, but no later than 24 hours, after learning of a pregnancy. Pregnancies must be reported directly to Allergan in the US and Canada, as listed on the Allergan Study Contacts Page and recorded on the Pregnancy Communication Form. Pregnancies in female partners of male patients occurring during the time frame described above must also be reported. The pregnancy will be followed until final outcome using the Pregnancy Notification Form and indicating that it is a follow-up report. The outcome, including any premature termination, must be reported directly to Allergan in the US and Canada. Pregnancy complications and elective terminations for medical reasons must be reported as an AE or SAE. Spontaneous abortions must be reported as an SAE. Any patient that becomes pregnant will be discontinued from the study.

If the patient agrees to have her primary care physician informed, the investigator should notify the patient's primary care physician that she was participating in a clinical study at the time that she became pregnant, and the investigator should provide the details of the treatment that the patient received (blinded or unblinded; [refer to Section 5.6.1 for information on unblinding], as applicable).

## **6.6 Laboratory Analyses**

The contract research organization central laboratory will perform all clinical laboratory tests, except urine pregnancy tests, which will be performed locally at the study site. The details related to sample handling, blood draw amounts, tubes, shipping, address, etc. are available in a separate laboratory manual.

Blood and urine samples for hematology, serum chemistry, serum lipase, and serum and urine pregnancy tests will be prepared using standard procedures.

Hematology and serum chemistry testing will be completed at screening, baseline (day 1), week 4, and all subsequent study visits through week 14 (posttreatment follow-up visit). Serum lipase testing will be performed at screening and baseline (day 1). Unscheduled blood draws for additional serum chemistry testing (lipase specifically) should be completed when possible for any patients with confirmed or suspected AEs of pancreatitis.

In addition, pregnancy tests will be performed for all women according to local procedures unless they are surgically sterile or there is a documented history of their postmenopausal status. A serum pregnancy test will be performed at screening and urine pregnancy tests will be performed at all other study visits through week 12 (or early withdrawal study visit), unless a serum pregnancy test is preferred at the discretion of the investigator or if required by local regulations. The serum pregnancy test will be performed by the central laboratory.

The blood samples will be used for the following tests:

Hematology: white blood cell count with differential, hemoglobin, hematocrit, platelet count, red blood cell count, mean corpuscular volume, mean corpuscular hemoglobin, and mean corpuscular hemoglobin concentration.

Serum Chemistry: albumin, alkaline phosphatase, ALT, AST, blood urea nitrogen, carbon dioxide, calcium (albumin corrected), chloride, creatinine, glucose, lactate dehydrogenase, phosphorus, potassium, sodium, total bilirubin\*, and total protein. Serum lipase will be tested at screening and baseline (day 1) only. Thyroid-stimulating hormone will be tested at screening only.

\*Note: If total bilirubin values are elevated in a patient who has received at least 1 dose of study drug, fractionated levels will also be determined if possible.

## **6.7 Sample Collections**

The details related to sample collection are provided in a separate laboratory manual.

## 7 Statistical and Analytical Plan

A statistical analysis plan (SAP) will be prepared and finalized before completion of the study. The plan document will provide further details regarding the definition of analysis variables and methodologies to meet all study objectives.

### 7.1 Primary Efficacy Endpoints

The primary efficacy endpoint is the proportion of primary composite responders determined over the 12-week double-blind treatment period. A primary composite responder is defined as a patient who meets the daily composite response criteria for at least 50% of days with diary entry during the interval from weeks 1 to 12.

A patient must meet BOTH of the following criteria on a given day to be a daily composite responder:

- Daily pain response: WAP score in the past 24 hours improved by  $\geq 40\%$  compared to baseline pain (average of daily WAP in the week prior to randomization).
- Daily stool consistency response: BSS score  $< 5$  (i.e., score of 1, 2, 3, or 4); or the absence of a bowel movement if accompanied by  $\geq 40\%$  improvement in WAP compared to baseline pain.

To be eligible to be a primary composite responder, a patient must have a minimum of 60 days of diary entries, including partial entries, over the interval from weeks 1 to 12. A partial diary entry consists of any of 3 data components: BSS score, WAP score, and bowel movement frequency. Partial entries will be used to determine whether or not a patient is a daily responder. Any patient with fewer than 60 days of diary entry will be considered a non-primary composite responder, including patients in the ITT analysis who recorded no post-baseline diary data.

### 7.2 Secondary Efficacy Endpoints

The following are the secondary efficacy endpoints:

- Proportion of stool consistency responders: defined as patients who meet the daily stool consistency response criteria (as defined in Section 7.1) for  $\geq 50\%$  of days with diary entries over a certain time period. This endpoint is defined for the 12-week treatment period, and for each 4-week interval (weeks 1 to 4, 5 to 8, and 9 to 12). For the weeks 1 to 12 time period, the  $\geq 50\%$  requirement is the same as specified for the primary efficacy endpoint in Section 7.1. For each of the 4-week periods, a responder must have a minimum of 20 days of diary entries over the 4 weeks.
- Proportion of pain responders: defined as patients who meet the daily pain response criteria (as defined in Section 7.1) for  $\geq 50\%$  of days with diary entries over a certain time period. This endpoint is defined for the 12-week treatment period, and each 4-week interval (weeks 1 to 4, 5 to 8, and 9 to 12). For the weeks 1 to 12 time period, the  $\geq 50\%$  requirement is the same as specified for the primary efficacy endpoint in Section 7.1. For each of the 4-week periods, a responder must have a minimum of 20 days of diary entries over the 4 weeks.
- Proportion of monthly composite responders: defined as patients who meet the daily composite response criteria (as defined in Section 7.1) for at least 50% of days with diary entry for a minimum of 20 days during each 4-week interval (weeks 1 to 4, 5 to 8, and 9 to 12).

[REDACTED]

[REDACTED]

[REDACTED]

[REDACTED]

[REDACTED]

[REDACTED]

[REDACTED]

[REDACTED]

[REDACTED]

[REDACTED]

[REDACTED]

[REDACTED]

[REDACTED]

[REDACTED]

[REDACTED]

[REDACTED]

[REDACTED]

[REDACTED]

[REDACTED]

[REDACTED]

[REDACTED]

[REDACTED]

[REDACTED]

[REDACTED]

[REDACTED]

[REDACTED]

[REDACTED]

[REDACTED]

[REDACTED]

[REDACTED]

[REDACTED]

[REDACTED]

[REDACTED]

[REDACTED]

[REDACTED]

[REDACTED]

[REDACTED]

[REDACTED]

[REDACTED]

[REDACTED]

[REDACTED]

[REDACTED]

## 7.5 Sample Size Calculations

Assuming a placebo response for the primary efficacy endpoint, composite response in pain and stool consistency rate at 12 weeks, of 13% and an approximate 14% treatment effect of eluxadoline over placebo, a sample size of 340 patients is required (1:1 randomization ratio, eluxadoline: placebo, 170 patients per arm). (From the Integrated Summary of Efficacy Report, patients refractory to loperamide in the pooled studies IBS 3001 and 3002 had 13% and 27% composite response in pain and stool consistency rates in the placebo and eluxadoline groups, respectively. This set of response rates are the same when using 40%

WAP improvement to replace the 30% in the primary efficacy composite responder criteria.) This sample size will have approximately 90% power to detect the difference of the primary efficacy endpoint response proportion between eluxadoline and placebo using a 2-sided chi-square test at a significance level of 0.05.

## 7.6 Analysis Sets

The following analysis sets will be used in the statistical analyses.

**Intent-to-Treat Population (ITT):** The ITT population will include all randomized patients. Patient disposition, demographics, and baseline characteristics and efficacy and HEOR data will be analyzed on the ITT population. Patients will be analyzed according to their randomization assignment, regardless of the actual treatment received. In this study, only randomized patients are considered as enrolled.

**Safety Population:** The Safety Population will include all patients enrolled who received at least 1 dose of study drug. Safety data will be analyzed using the safety population. Patients will be grouped and analyzed according to the treatment they will actually receive.

## 7.7 Statistical Analysis Methodology

Statistical analysis will be performed using [REDACTED]  
[REDACTED] Continuous variables will be summarized using mean, standard deviation, median, minimum value, and maximum value. Categorical variables will be summarized using frequency counts and percentages. Data will be listed in patient listings.

All statistical tests will be 2-sided at significance level of 0.05.

No adjustment for the multiplicity of the endpoints will be performed since there is only a primary efficacy endpoint and no interim analyses have been planned.

Statistical analysis and methodologies will be briefly discussed in sections below. All details of the statistical analyses, methods, and missing data handling strategy will be described in the study SAP.

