### 7.7.2 Analysis of Secondary Efficacy Endpoint

The proportions of stool consistency responders and pain responders (defined in Section 7.2) over the 12-week treatment period and at each 4-week interval (weeks 1 to 4, 5 to 8, and 9 to 12) will be analyzed similar to the primary endpoint analysis.

The proportion of monthly composite responders (defined in Section 7.2) at each 4-week interval (weeks 1 to 4, 5 to 8, and 9 to 12) will be analysed similar to the primary endpoint analyses.

[REDACTED]

[REDACTED]

[REDACTED]

[REDACTED]

[REDACTED]

[REDACTED]

[REDACTED]

[REDACTED]

[REDACTED]

[REDACTED]

[REDACTED]

[REDACTED]

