### **7.7.7 Interim Analyses**

There will be no interim analysis for this study.

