5. Duration to Study Treatment(s) and Compliance of Treatment.....	11

6.3 Primary Efficacy Analyses	14
-------------------------------------	----

6.3.1 Primary Analyses for Primary Efficacy Endpoint.....	15
---	----

[figure not shown]
6.3.2 Other Analysis for Primary Efficacy Endpoint 15
6.4 Secondary Efficacy Analyses 15

8. Interim Analyses 22
9. Deviations from Protocol 22
10. Appendices 24

10.2 Bristol Stool Scale 28

11. Signature Page 70

1. Introduction

The analyses described in the SAP are based upon the final protocol dated 12 August 2016. Where differences exist between analyses specified in the protocol and this SAP, the SAP will be followed.

This is a Phase 4, multicenter, multinational, randomized, double-blind, placebo-controlled, parallel group study to evaluate the efficacy, safety, and tolerability of eluxadoline 100 mg BID in patients with IBS-D who report that use of loperamide to treat their IBS-D symptoms in the prior 12 months failed to adequately control their symptoms of IBS-D. (RELIEF)

Approximately 340 patients will be randomly assigned (in a 1:1 ratio) to 1 of 2 treatment groups below:

- Group 1: eluxadoline 100 mg oral tablets BID with food
- Group 2: matching placebo oral tablets BID with food

During the screening period (up to 1 week), screening procedures, including Prior Symptoms Management Questionnaire (refer to Appendix 10.7), will be performed. After that, eligible patients will enter a pretreatment period (up to 3 weeks). At the beginning of the pretreatment period, patients will receive instructions for completing an electronic patient-reported outcome (ePRO) diary to collect daily information related to their IBS-D symptoms and use of loperamide rescue medication. At the end of the pretreatment period, patients who meet the study inclusion criteria related to ePRO diary compliance, stool consistency (Bristol Stool Scale [BSS]), average worst abdominal pain (WAP) score, and use of loperamide rescue medication will be randomized into a 12-week double-blind treatment period via central randomization.

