6.4 Secondary Efficacy Analyses

[figure not shown]
The following are the secondary efficacy endpoints:

- Proportion of stool consistency responders: defined as patients who meet the daily stool consistency response criteria (BSS <5, or absence of a bowel movement) for $\geq 50\%$ of days with diary entries over a certain time period. This endpoint is defined for the 12-week treatment period and for each 4-week interval (week 1 to 4, 5 to 8, and 9 to 12). For the 12-week treatment period, the $\geq 50\%$ requirement is the same as specified for the primary efficacy endpoint in Section 6.3. For each of the 4-week intervals, a responder must have a minimum of 20 days of diary entries over the 4 weeks. Any patient with fewer than 60 days (for 12-week period) or with fewer than 20 days (for 4-week interval) of diary entries will be considered as a non-responder.

- Proportion of pain responders: defined as patients who meet the daily pain response criteria (as defined in Section 6.3) for $\geq 50\%$ of days with diary entries over a certain time period. This endpoint is defined for the 12-week treatment period and for each 4-week interval (week 1 to 4, 5 to 8, and 9 to 12). For the 12-week treatment period, the $\geq 50\%$ requirement is the same as specified for the primary efficacy endpoint in Section 6.3. For each of the 4-week intervals, a responder must have a minimum of 20 days of diary entries over the 4 weeks. Any patient with fewer than 60 days (for 12-week period) or with fewer than 20 days (for 4-week interval) of diary entries will be considered as a non-responder.
- Proportion of monthly composite responders: defined as patients who meet the daily composite response criteria (as defined in Section 6.3) for at least 50% of days with diary entry for each 4-week interval (week 1 to 4, 5 to 8, and 9 to 12). For each of the 4-week intervals, a responder must have a minimum of 20 days of diary entries over the 4 weeks. Any patient with fewer than 20 days of diary entries for the 4-week interval will be considered as a non-responder.

The secondary endpoints will be analyzed by the number and percentage of the corresponding responders with p-value from chi-square test to test the different response rates between treatment groups. No adjustment for the multiplicity of the endpoints will be performed.

[figure not shown]

[figure not shown]
8. Interim Analyses

[figure not shown]
There will be no interim analysis for this study.

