9. Deviations from Protocol

[figure not shown]
This analysis mentioned in protocol section [7.7.3](#), “The mixed-effect model for repeated measures method will be used to analyze these endpoints with treatment group as the factor and baseline endpoint values as covariate.” is not performed.

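### Do the 11 unadjusted secondary tests need a testing order, a gate behind the primary, or a nominal label?

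*Protocol*

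**What the plan says.** Protocol 7.7 sets one level for everything: "All statistical tests will be 2-sided at significance level of 0.05". It then waives adjustment: "No adjustment for the multiplicity of the endpoints will be performed since there is only a primary efficacy endpoint and no interim analyses" are planned. Protocol 7.7.7 confirms the second half of that reason: "There will be no interim analysis for this study".

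Protocol 7.2 defines three kinds of secondary responder. Of the stool consistency endpoint it says "This endpoint is defined for the 12-week treatment period, and for each 4-week interval"; the pain endpoint has the same four periods. The monthly composite is defined for the three 4-week intervals only. Under Protocol 7.7.2 the stool and pain proportions "will be analyzed similar to the primary endpoint analysis", and the monthly composite is treated likewise. SAP 6.4 gives each a chi-square p-value and repeats, without a reason, "No adjustment for the multiplicity of the endpoints will be performed".

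Hypotheses H0 and HA are written once, for the primary composite responder rate (Protocol 7.7.1, SAP 6.3.1). Nothing comparable is written for any secondary endpoint.

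**The concern.** The stated reason is true but narrow. One primary endpoint analysed once needs no adjustment. That says nothing about a further family of comparisons run at the same level. The Statistical Methods entry of the Protocol Synopsis sharpens the point: it puts the composite and the 12-week pain-alone and stool-alone comparisons in one sentence, at the same 0.05, with no ranking.

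The awkward case is a non-significant composite alongside p<0.05 for pain alone or stool alone over 12 weeks. The visible text does not say what status that result would have. If the report settled the matter after seeing the data, a chance finding on one component could be presented as if it were a confirmed effect.

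**Working it through.** **Primary test, the plan's own figure.** Inputs from Protocol 7.5: 13% v 27%, 170 per arm, two-sided chi-square at 0.05.

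- Pooled rate (0.13 + 0.27)/2 = 0.20; null SE = √(2 × 0.20 × 0.80/170) = 0.0434.
- Alternative SE = √(0.13 × 0.87/170 + 0.27 × 0.73/170) = 0.0427.
- Power = Φ((0.14 − 1.960 × 0.0434)/0.0427) = Φ(1.287) = 0.901.

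This reproduces the stated 90%. With one endpoint and no interim look, the primary type I error is 0.05. The secondary tests alter neither figure.

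**Count of secondary tests.** Stool 4 + pain 4 + monthly composite 3 = 11. Two of these are 12-week components; the other nine are 4-week comparisons.

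**Chance findings with no true effect.** If the 11 tests were independent the figure would be 1 − 0.95^11 = 43%, which is too high for endpoints built from overlapping diary days. The documents give no correlations, so a common correlation ρ of 0.5 to 0.9 between test statistics is assumed. For k tests:

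F(k) = 1 − ∫ [Φ((1.96 − √ρ·c)/√(1−ρ)) − Φ((−1.96 − √ρ·c)/√(1−ρ))]^k φ(c) dc

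For results favouring eluxadoline only, drop the second Φ term; each test then has error 0.025. The chance that the primary misses while at least one of k secondaries succeeds is F(k+1) − 0.05 two-sided, or F(k+1) − 0.025 in one direction.

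| Event under no effect | ρ = 0.9 | ρ = 0.5 |
|---|---|---|
| Any of 11, two-sided | 13.1% | 30.4% |
| Any of 11, favouring eluxadoline | 6.6% | 15% |
| Either 12-week component, two-sided | 7.0% | 9.1% |
| Either 12-week component, favouring eluxadoline | 3.5% | 4.5% |
| Primary misses, a 12-week component succeeds, two-sided | 3.4% | 7.5% |
| Same, favouring eluxadoline | 1.7% | 3.8% |

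A common correlation is a simplification, because these endpoints mix overlapping and separate time windows. A simulation of 84-day diaries under assumed patient variation and pain-stool correlation gives somewhat higher two-sided figures: 19% to 34% for any of 11, and 5% to 8% for a component without the primary. The directional version of the latter is about half, 2.5% to 4%.

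**What formal control would do.** Gating behind the primary leaves N and primary power alone, but at the planned effect the gate stays shut in 1 − 0.901, about 10%, of trials. Bonferroni over 11 tests uses 0.05/11 = 0.0045 each; an effect of the primary's size would then have power Φ((0.14 − 2.838 × 0.0434)/0.0427) = 65%. Calling the p-values nominal changes no figure.

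**The case for a change.** The case for a change is respectable. Unadjusted secondary tests are usually accepted because they are labelled nominal or held behind the primary, and the visible text does neither. Disclosing that there is no adjustment does not say how the results will be read, and the reason given does not apply to these tests. The Synopsis sentence invites a reader to treat the 12-week components as equals of the composite. A line in SAP 6.4 would be cheap, and the SAP's own precedence rule allows it: "Where differences exist between analyses specified in the protocol and this SAP, the SAP will be followed".

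Some of this stands. The reason in Protocol 7.7 is incomplete as written, the two-sided family error exceeds 5% at every correlation considered, and the visible text leaves a component result after a failed composite without a stated status.

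Three things limit it. First, no order, gate or label is established only for the visible text: Protocol 7.3 to 7.4 and 7.7.3 to 7.7.5 are redacted, SAP 6.1, 6.2 and 6.5 are not shown, and any of them could carry a label. Second, the feared outcome is a false claim for eluxadoline, and half of the two-sided chance findings favour placebo. Third, the harm requires the report to rest a claim on a secondary endpoint, which no visible section plans. A fixed sequence or Holm procedure would therefore replace a disclosed choice with a different inferential strategy, rather than correct a mistake.

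**Conclusion.** No change is called for. If the plan is followed as written, the primary conclusion is sound: one test, one look, error 0.05, power 90.1% with 170 per arm.

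The gap concerns how the secondary p-values are read, and the plan's structure supplies the ordinary answer. Only the composite has formal hypotheses, and both documents say the remaining tests are unadjusted. A trained reader takes such p-values as supportive and would not accept a component result as confirmation after a failed composite. A sentence saying so would only write down that convention. A gate with a fixed order is a sponsor's option on which reasonable statisticians differ, particularly in a Phase 4 study of an already marketed dose.

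The exposure is modest for the case that matters most: with no true effect, a 12-week component favours eluxadoline without a primary win in 1.7% to 3.8% of trials. That rests on an assumed common correlation of 0.9 to 0.5; the diary simulation suggests about 2.5% to 4%. The larger figures, 13% to 30% for any of the 11 in either direction, are driven mainly by the nine 4-week comparisons and are a reason for caution in reading isolated results.
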